September 10, 2019

US Department of Health and Human Services
[name]
[name]

PRINCIPAL INVESTIGATOR : [name]
TITLE : TrueTear in Sjogren's Disease Patients
PROTOCOL # : 830076

The following document spells out the study protocol and statistical analysis plan for this trial.

Sincerely,

[name]
Research Coordinator

Protocol

In this trial, the protocol is straightforward. The study consists of two visit days for the patient. The first day is considered the screening day. On the first day, a baseline Schirmer's test is performed after the patient's eyes have been anesthetized. The duration of this test is five minutes. At the end of the five minutes, the tear production is measured using the Schirmer strips. The patient must produce ten millimeters or less in at least one eye to qualify for the study. Next, the TrueTear device is simulated using two cotton swabs. One cotton swab is inserted into each nostril. Using Schirmer strips to measure tear production, the patient swirls the cotton swabs around in their nostrils until they produce four millimeters above their baseline in at least one eye. The patient is then to hold the cotton swabs in their nose for the remainder of the five minutes. In order to qualify for the study, the patient must produce four millimeters or greater in the study eye. In instances where the patient is of child-bearing age, a pregnancy test is performed to ensure that the patient is not pregnant.

After visit one, visit two can be completed the following day or any day during the next forty-five days. During visit two, the effectiveness of the device is tested. The patient is randomized to which application method, internal or external, is used first. During both the first and second applications, Schirmer strips are used to measure tear production over the course of five minutes. For the first three minutes, the device is used. For the remaining two minutes, the device is removed. Between the first and second applications, there must be a waiting period of at least forty-five minutes. This break ensures that the patient's tear glands have enough time to restore. This is necessary for accurate measurement of the effectiveness of the device.

Statistical Analysis Plan

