Our plan to analyze the data from this trial will involve a few different comparisons, as well as factoring in a few different variables. First, we will look to compare both the internal and external stimulation results to the baseline results. When making these comparisons, the order in which application method was used first will be factored in. This will help us determine whether or not the order of application methods impacts the final results. Next, we will examine each stimulation method (cotton swabs, internal application with TrueTear device, and external application with TrueTear device) relative to baseline to see if the changes are statistically significant from baseline, and to determine an estimated mean change. We also plan to compare each application method to each other to determine if there is a statistically significant difference. While making the comparison, we also want to separately account for two different factors, patients on Sjogren's medication vs. patients not on Sjogren's medication and patients with a baseline Schirmer of less than 5 mm. vs. patients with a baseline Schirmer of greater than or equal to 5 mm. In a similar fashion, we also want to examine each application method individually to determine the p-value, confidence interval, mean, and standard deviation.

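### Order is named only in the method-versus-baseline comparisons, where its effect is a between-patient contrast; a within-patient period estimate from the same data should be added as the main test of a common order effect

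*Combined protocol and SAP*

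**What the plan says.** The Protocol section describes a two-period, two-sequence crossover within visit two. On allocation it says: "The patient is randomized to which application method, internal or external, is used first". Every patient receives both methods, and on the gap between them it says: "Between the first and second applications, there must be a waiting period of at least forty-five minutes". The only baseline described is from the screening day: "On the first day, a baseline Schirmer's test is performed after the patient's eyes have been anesthetized".

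The Statistical Analysis Plan opens its list of comparisons with "First, we will look to compare both the internal and external stimulation results to the baseline results". It then adds "When making these comparisons, the order in which application method was used first will be factored in" and gives the purpose: "This will help us determine whether or not the order of application methods impacts the final results". No model or test is named for this step.

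A later sentence covers the comparison between methods: "We also plan to compare each application method to each other to determine if there is a statistically significant difference". The sentence after it begins "While making the comparison, we also want to separately account for two different factors" and lists Sjogren's medication status and baseline Schirmer category (below 5 mm, or 5 mm and above). Order and period are not listed there.

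**The concern.** The plan poses the order question itself, so the analysis that answers it matters. Within one method-versus-baseline comparison, a patient used that method either first or second, never both. An order term there can only compare one randomized group with the other, and it carries the spread between patients. Yet each patient supplies both a first and a second reading at visit two, so a first-versus-second effect common to the two methods can be estimated within patients.

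Two things follow.

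- The plan's order result may be much less precise than its own data allow, and a non-significant result could be misread as showing that order has no effect.
- A chance difference in response between the two order groups enters the internal and external order contrasts with opposite signs. The two can therefore point in different directions, and the plan has no rule for reading them together.

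**Working it through.** The plan states no figure for this step, so there is none to reproduce.

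**Inputs.** From the documents: two methods per patient, randomized order, one screening baseline. Assumed, because the documents are silent: equal group sizes, here 15 + 15 = 30 patients; device-reading SD 6 mm for both methods; baseline SD 3 mm; device-baseline correlation *a* = 0.5 (range 0.3 to 0.7); internal-external correlation *c* = 0.6 (range 0.2 to 0.8).

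**Step 1: what the order contrasts are.** Let group A be internal-first and group B external-first, with group means I, E and b (baseline). Written as first minus second:

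- internal contrast: D_I = (I_A − b_A) − (I_B − b_B)
- external contrast: D_E = (E_B − b_B) − (E_A − b_A)

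Both compare different patients. Their average is ½[(I_A − E_A) + (E_B − I_B)]. Baseline cancels, and what remains is the equally weighted mean over the two groups of each patient's first-minus-second difference, which is the within-patient estimate. If D_I and D_E have equal variance, their average cannot have a larger variance than either one. The within-patient estimate is then never less efficient for a common order effect, whatever the sample size.

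**Step 2: standard errors at the central values.**

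- Variance of change from baseline = 36 + 9 − 2 × 0.5 × 6 × 3 = 27.
- Between-patient SE = √(27/15 + 27/15) = √3.60 = 1.90 mm.
- Within-patient SE = √(2 × 36 × (1 − 0.6)/30) = √0.96 = 0.98 mm.
- Variance ratio = 3.60/0.96 = 3.75.

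**Step 3: range.** With these SDs the ratio is (2.5 − 2*a*)/(1 − *c*), and sample size drops out:

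- *a* = 0.7, *c* = 0.2: 1.1/0.8 = 1.4
- *a* = 0.5, *c* = 0.6: 1.5/0.4 = 3.75
- *a* = 0.3, *c* = 0.8: 1.9/0.2 = 9.5

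Using baseline as a covariate instead of change scores gives 2(1 − *a*²)/(1 − *c*), that is 1.02/0.8 = 1.3, 1.5/0.4 = 3.75 and 1.82/0.2 = 9.1 at the same three points. Adjustment does not remove the loss.

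**Step 4: agreement of the two contrasts.** Covariance of the two changes = 0.6 × 36 − 9 − 9 + 9 = 12.6, so D_I and D_E correlate −12.6/27 = −0.47. In simulation at the central values with a true common effect of 2 mm, they had opposite signs in about 28% of trials.

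**The case against.** **The SAP does not fix the model.** It says only that order will be factored in. One repeated-measures model of baseline, internal and external readings would fit that wording and would use the within-patient information. This stands: the between-patient reading is the natural one, but the text does not impose it. It is also a reason to write the model down.

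**A reader might infer that the plan will usually miss an order effect.** The documents do not support that, because sample size, SDs, correlations, alpha and effect size are all absent. With the assumed 30 patients and two-sided 0.05, one method-specific test has 17% power at 2 mm, against 50% within patients, and 33% against 84% at 3 mm. But the plan makes two such comparisons. The chance that at least one signals is about 34% at 2 mm and 60% at 3 mm, with a false-positive rate of about 9%. Larger samples or effects raise all of these. These figures illustrate one invented scenario and are not properties of the plan.

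**A reader might infer that the order check licenses combining first and second applications.** No passage ties a pooling decision to it. With equal group sizes, a common period effect also cancels from the mean internal-external difference, so no biased result has been shown.

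**Replacing the method-specific contrasts would lose information.** This stands. The averaged estimate halves an effect present in one method only and cancels effects of opposite direction. Under the same assumptions, if second use lowers external by 4 mm and leaves internal unchanged, the external contrast has 53% power and the averaged estimate 50%. If second use lowers external by 3 mm and raises internal by 3 mm, each method-specific contrast has 33% power and the averaged estimate 5%, which is no more than its false-positive rate. The within-patient estimate should be added to these contrasts and should not displace them.

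**Conclusion.** The point holds as an efficiency loss with a ready remedy. The SAP asks about order but names it only in the baseline comparisons. Read naturally, each of those gives a between-patient contrast, with variance about 1.4 to 9.5 times that of the within-patient estimate for a common first-versus-second effect (3.75 at the central values). That size rests on the assumed SDs and correlations and on equal allocation. The direction needs only that the two method-specific contrasts have equal variance.

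The advantage is confined to an order effect shared by both methods. Unequal carryover is a between-patient quantity under any analysis of this two-period design, and it cannot be separated from a method-by-period interaction.

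**What to change.** Add to the Statistical Analysis Plan:

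1. A joint analysis of the two visit-two readings with patient, method and period terms. An equivalent is each patient's first-minus-second difference, averaged within each order group and then over the two groups with equal weight. Report the period effect in mm with a 95% CI and p-value, as the main test for a common order effect.
2. The internal-versus-external comparison taken from the same model. This protects it if the order groups end up unequal, and keeps any period effect out of its error term.
3. The internal and external order contrasts against baseline, retained with CIs as supporting results for an order effect that differs by method.
4. A statement that unequal carryover can be estimated only between patients in this design, and that a non-significant order result is not evidence that order has no effect.

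The cost is a few sentences of SAP text. No new data, procedure or patients are needed.

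### If qualifying patients' study eyes are analysed, the swab-versus-baseline test reuses the screening readings that decided entry: significance is forced if the 4 mm rule means a rise over baseline, and can be inflated if it means an absolute reading

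*Combined protocol and SAP*

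**What the plan says.** In the Protocol section, visit one supplies the baseline and the swab reading: "The first day is considered the screening day". Both readings bear on eligibility.

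- Baseline: "The patient must produce ten millimeters or less in at least one eye to qualify for the study".
- Swab procedure, run to a target: "the patient swirls the cotton swabs around in their nostrils until they produce four millimeters above their baseline in at least one eye". The swabs are then held still for what is left of the five minutes.
- Swab entry rule: "In order to qualify for the study, the patient must produce four millimeters or greater in the study eye". This sentence does not say whether its 4 mm is a total reading or a rise. It refers to a study eye, which is not defined, whereas the procedure refers to either eye.

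Visit two is given to the device: "During visit two, the effectiveness of the device is tested". Only internal and external applications are described there, with no repeat baseline and no repeat swab reading.

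The Statistical Analysis Plan opens with the device: "First, we will look to compare both the internal and external stimulation results to the baseline results". It continues: "Next, we will examine each stimulation method (cotton swabs, internal application with TrueTear device, and external application with TrueTear device) relative to baseline", asking for significance and an estimated mean change. It then adds: "We also plan to compare each application method to each other to determine if there is a statistically significant difference". Whether swabs count as a method in that last comparison is not stated. The SAP does not define the analysis set or the analysed eye, does not say what happens to screen failures, and does not mention selection on the screening readings.

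**The concern.** A test of change from baseline asks whether the observed change could have arisen by chance. If patients are analysed only because that same reading was high enough, the test no longer answers the question. A significant swab change could then be reported as a finding when the entry rule forced or favoured it, and it would sit beside the device results as if equally interpretable.

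The same selection reaches two other comparisons. Device-versus-baseline, which the SAP lists first, uses a baseline that helped decide entry. Any swab-versus-device test sets a selected reading against an unselected one.

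**Working it through.** The plan states no sample size, SD, effect or power, so there is no figure of its own to reproduce.

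**Inputs from the Protocol section.** Baseline limit 10 mm; 4 mm swab rule; swab and baseline read at visit one only; device read at visit two only.

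**Assumed, not in the documents.** Analysis of qualifying patients' study eyes, with the study eye meeting the baseline limit; strip length 35 mm; true tear level gamma-distributed with mean/SD 4/3, 6/4 or 8/6 mm; reading-error SD 1.5 to 4 mm; n = 10 for rejection rates.

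**Step 1. Rise-over-baseline reading: arithmetic.** Every analysed change is at least +4 mm, so the mean cannot be below 4 mm.

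- Sign test, all changes positive: p = 2 × 0.5^n. n = 5 gives 0.0625; n = 6 gives 0.031.
- t-test, least favourable data at these small n: one change at 35 mm and the rest at 4 mm. Mean = 4 + 31/n and standard error = 31/n, so t = 1 + 4n/31. At n = 9, t = 2.16 and p = 0.063. At n = 10, t = 2.29 and p = 0.048.

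No assumption about tear distribution or swab effect is needed here.

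**Step 2. Both readings: simulation with independent reading errors.** Readings are clipped to 0 to 35 mm and eyes with baseline of 10 mm or less are kept. "Inert" means no true effect. False positives are two-sided 5% t-tests that favour the swab (nominal 2.5%). Ranges run over the assumed tear levels and error SDs.

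| Quantity | Rise over baseline | Absolute 4 mm |
|---|---|---|
| Inert swab, mean change | 4.8 to 7.1 mm | 0.7 to 3.6 mm |
| of which added by the swab rule | 4.6 to 6.1 mm | 0.55 to 2.9 mm |
| False positives, inert swab | forced (Step 1) | 17% to 75% |
| Added by the rule, true swab effect 5 mm | 1.0 to 3.3 mm | 0.04 to 1.15 mm |
| Added by the rule, true swab effect 10 mm | 0.01 to 1.1 mm | 0.00 to 0.18 mm |
| Inert device minus baseline, inert swab | +2.1 to +3.4 mm | +0.1 to +1.6 mm |
| Inert device minus baseline, swab effect 5 mm | +0.6 to +2.3 mm | +0.05 to +1.3 mm |
| Inert swab minus inert device | 2.5 to 4.0 mm | 0.45 to 2.65 mm |
| Inert internal minus inert external | within about 0.02 mm of 0 | within about 0.02 mm of 0 |

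The baseline limit alone, with no swab rule, gives an inert swab +0.05 to +1.2 mm. With error SD 0.5 mm, an inert swab under the absolute reading shows about 0.1 mm and 5% to 6% false positives.

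**Step 3. Is reuse of the entry readings the cause?** In a second model (normal tear levels, mean 5 or 8 mm, SD 3 or 4 mm, error SD 1 to 4 mm), an inert swab showed 4.4 to 7.2 mm (rise) and 0.3 to 3.6 mm (absolute) on the entry readings. Fresh readings in the same qualifying patients gave about 0 mm and 4% to 6% two-sided rejection.

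**Step 4. Shared day effect.** Baseline and swab are read on the same day, so their errors may be partly common. Take the same total error SD, with 50% or 80% of its variance shared within a day (assumed shares), the absolute reading and an inert swab:

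| Quantity | Independent | 50% shared | 80% shared |
|---|---|---|---|
| Added by the swab rule | 0.55 to 2.9 mm | 0.28 to 1.87 mm | 0.11 to 0.87 mm |
| False positives | 17% to 75% | 10% to 49% | 6% to 22% |
| Inert device minus baseline | +0.1 to +1.6 mm | -0.37 to +0.92 mm | -0.97 to +0.28 mm |

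The device bias can change sign because an absolute swab rule favours patients having a good day at visit one, which also raises their baseline. With a 5 mm swab effect it stayed positive. Under the rise-over-baseline reading it was positive in every setting run.

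**The case against.** The strongest reply is that the concern rests on matters the documents leave open: who is analysed, which eye, and what the 4 mm means. If every swab-tested patient were analysed, the entry selection would disappear. This stands, and it is why the point is conditional. It is not a full answer, because the SAP does not commit to that population, and swirling to a target would still tie the stimulus to the outcome.

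Second, the largest figures assume an inert swab, which is unlikely for a procedure meant to imitate the device. Under the rise-over-baseline reading, only 2% to 26% of those tested would then qualify. An inert swab is the right null for judging whether a p-value is valid, but it is not a forecast. With a 10 mm swab effect the rule adds little. The model also uses one eye and a fixed effect, and so leaves out the either-eye wording and the swirling to target.

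Third, independent errors are a material assumption. Step 4 shows that relaxing it shrinks the swab bias under the absolute reading and can reverse the device bias. That stands.

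Fourth, effectiveness is tested at visit two and the swab is a screening step. That limits the weight of the swab result, but the SAP still lists it for significance testing.

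A reader might go further and infer that the swab p-value is worthless on any reading, that device changes from baseline are always overstated, or that swabs do not work. The documents support none of these. Under the absolute reading the distortion can be negligible, the device bias has no fixed sign there, and a test compromised by selection is not evidence of no effect.

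**Conclusion.** The point holds, on the condition that qualifying patients' study eyes are analysed.

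- **Rise-over-baseline reading (high confidence).** Significance is guaranteed by entry from n of about 6 (sign test) to 10 (worst-case t-test, 35 mm strip assumed). The p-value carries no information about the swab.
- **Absolute reading (medium confidence).** Significance is not forced. The mean and false-positive rate are inflated by an amount that depends on reading error, on how much of it baseline and swab share on the day, and on the true swab effect. The bias is near zero when the effect is large or the error small.
- **Device versus baseline.** Biased upward in all settings run under the rise-over-baseline reading. Under the absolute reading with little or no swab effect, the direction is not established once readings share a day effect.
- **Swab versus device.** Also affected, if the SAP intends that comparison.
- **Internal versus external.** Not biased this way, since neither reading was used for entry and the comparison does not use the baseline.

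All sizes in millimetres and all rejection rates are illustrative, because the documents give no SD, n or screen-failure rate. This should be fixed, but it does not undermine the randomised device comparison.

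**What to change.** Amend the wording as follows.

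1. Remove cotton swabs from the methods tested for significance against baseline, and from any between-method significance test.
2. Report the swab change descriptively (n, mean, SD, range) as a screening characteristic, and state that it was an entry criterion.
3. Reconcile the two 4 mm sentences in the Protocol section (the swirling target and the entry rule), so that it is clear whether entry turns on a rise or a total reading, and in which eye.
4. State the analysed eye and the analysis set, including how screen failures are handled.
5. State that device-versus-baseline estimates use a baseline that was part of entry selection and may be biased, including by regression to the mean.

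An analysis of all swab-tested patients, if their readings were kept, can be added as supplementary.

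The cost is text only: no new data or visits. What is lost is a swab p-value that cannot be interpreted. The internal-versus-external comparison is unchanged.

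### If single-method change from baseline is reported by the 5 mm baseline split, regression to the mean biases the result toward a larger effect in drier patients

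*Combined protocol and SAP*

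**What the plan says.** The Statistical Analysis Plan section describes three steps that matter here.

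- Each method (swabs, internal, external) is examined "relative to baseline to see if the changes are statistically significant from baseline, and to determine an estimated mean change". No split is mentioned.
- The methods are then compared: "We also plan to compare each application method to each other to determine if there is a statistically significant difference". The two factors are introduced in this comparison: Sjogren's medication use, and "patients with a baseline Schirmer of less than 5 mm. vs. patients with a baseline Schirmer of greater than or equal to 5 mm".
- The section closes: "In a similar fashion, we also want to examine each application method individually to determine the p-value, confidence interval, mean, and standard deviation".

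The Protocol section describes one baseline reading: "On the first day, a baseline Schirmer's test is performed after the patient's eyes have been anesthetized". The same reading is used for entry: "The patient must produce ten millimeters or less in at least one eye to qualify for the study". The device is tested later: "visit two can be completed the following day or any day during the next forty-five days". No repeat baseline and no unstimulated or sham reading at visit two is described. The SAP mentions no interaction test and no allowance for error in the baseline.

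**The concern.** The closing sentence of the SAP most naturally carries the two factors into the single-method results; otherwise it largely repeats the change analysis already described. A p-value for one method alone needs a reference, and baseline is the only one the SAP names. On that reading, the outcome is change from baseline by the 5 mm split.

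An error in the visit-one reading then enters twice, with opposite signs. A patient who reads low by chance is more likely to fall below 5 mm and to show a large rise at visit two. A patient who reads high by chance is more likely to fall at 5 mm or above and to show a small one. Without an unstimulated visit-two reading, the data cannot separate this from a real difference by severity. The trial could report that the device works better in drier patients when it does not, or hide a real trend the other way.

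**Working it through.** **Inputs from the documents.** Cut at 5 mm; entry at 10 mm or less; one baseline reading; both device readings at visit two. The documents state no SD, effect size or test-retest reliability, so there is no planned figure to reproduce. All values below for these quantities are assumptions.

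**Closed form.** Let T be the patient's true level, baseline B = T + e1, internal reading I = T + d + e2, with the same effect d for everyone and independent errors. Under normality, with mean m and reliability r (true variance over total variance):

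E(I − B | B) = d − (1 − r)(B − m)

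so the spurious gap is

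(mean change below 5) − (mean change at 5 or more) = (1 − r) × (mean B at 5 or more − mean B below 5).

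Take m = 5, total SD 3 and B restricted to 0–10 mm. The limits lie 5/3 = 1.667 SD from the mean. Mean B in the upper group exceeds 5 by 3 × (0.3989 − 0.0995)/(0.9522 − 0.5) = 1.99 mm. By symmetry the two groups differ by 3.97 mm. The gap is therefore:

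- r = 0.5: 0.5 × 3.97 = 1.99 mm
- r = 0.7: 0.3 × 3.97 = 1.19 mm
- r = 0.9: 0.1 × 3.97 = 0.40 mm
- r = 1.0: 0

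Simulation of the same model with d = 5 gave 1.99, 1.20, 0.40 and 0.00 mm. At r = 0.7 the uniform 5 mm effect appears as 5.60 versus 4.40 mm.

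**Simulation by error SD.** T is the absolute value of a normal variate; B = T + error, floored at 0; I = T + 6 + independent error; patients are kept if B is 10 or less. The last row adds an entry rule requiring a swab reading at least 4 mm above baseline, with a swab effect also set at 6 mm. Entries are gaps in mm.

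| Assumed true mean, SD | error SD 0.5 | 1 | 1.5 | 2 | 3 |
|---|---|---|---|---|---|
| 5, 3 | 0.1 | 0.4 | 0.9 | 1.4 | 2.5 |
| 6, 4 | 0.1 | 0.3 | 0.6 | 1.0 | 2.0 |
| 5, 3, with swab rule | 0.1 | 0.4 | 0.7 | 1.1 | 2.0 |

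If the swab rule is instead read as 4 mm in total, the gaps barely change.

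**Within each group.** With mean 5, SD 3 and error SD 2, the uniform 6 mm effect appears as 6.75 mm below the cut and 5.33 mm at or above it. The within-group biases are 6.75 − 6 = +0.75 and 5.33 − 6 = −0.67 mm. They are the same size when the device effect is set to zero, so a test of change against zero inside a stratum is affected too.

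**Where the artefact is small or masked.** With error proportional to tear level, a skewed (gamma) model with mean 6 and SD 3.5 gave gaps of 0.05 mm at an error CV of 0.1 and 0.99 mm at a CV of 0.5. If the true response rises by 0.5 mm per mm of tear level (mean 5, total SD 3), the observed gap is +1.0, −0.2 and −1.4 mm at reliability 0.5, 0.7 and 0.9.

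**The method contrast.** With internal set 2 mm above external, I − X = (T + d + e2) − (T + d − 2 + e3) = 2 + e2 − e3. Baseline does not appear. The simulated difference was 2.0 mm in both groups in every setting.

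**The case against.** The strongest objection is textual. The 5 mm split is introduced for the comparison of methods, where baseline cancels within patient and no such bias exists. Reaching change from baseline by stratum takes inferences the SAP does not spell out: that the closing sentence carries the factors over, that its outcome is change, and that the strata will then be compared. Accounting for a factor could also mean adjustment. This stands: a reader might infer that the SAP explicitly plans a stratified change analysis, and it does not. The point is therefore conditional. The ambiguity still needs resolving, because the natural reading leads to the biased analysis.

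A second objection is that the size is unknown and could be trivial. This also stands. At an error SD of 0.5 to 1 mm the gap is 0.1 to 0.4 mm, and with proportional error it can be near zero.

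A third is that a test of change within one stratum asks a different question from the gap between strata. It does, but the within-stratum means carry the same bias, so the tests are not protected.

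Finally, the argument does not reach medication. Those groups are not formed from the noisy Schirmer reading, so regression to the mean gives no reason to drop single-method results by medication.

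**Conclusion.** The point holds conditionally. If single-method change from baseline is reported by the 5 mm split, change is biased upward below 5 mm and downward at 5 mm or more. The resulting gap is about 0.1 to 2.5 mm for error SDs of 0.5 to 3 mm, given a constant effect, error of constant size and a true mean of 5 mm with SD 3 mm. It is somewhat smaller if entry requires a swab response 4 mm above baseline, and zero only if the baseline is free of error. None of these inputs is in the documents.

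Two stronger readings are not supported. One is that the split invalidates the comparison of internal with external application; that contrast is unaffected. The other is that drier patients will necessarily show a larger effect, or that any larger effect seen in them must be spurious. The artefact pushes in that direction, but a real trend may add to it or outweigh it, and the planned data cannot tell them apart.

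**What to change.** State in the SAP that the baseline-Schirmer factor is tested only through the visit-two internal-minus-external difference. Use one method-by-baseline interaction with baseline Schirmer as a continuous variable, and keep the 5 mm split for display. For each method alone, show visit-two readings by baseline group descriptively. Do not test or interpret change from baseline, within or between the two baseline groups, as evidence that the effect differs by severity.

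Single-method results by medication may stay. Any claim that the effect differs by medication should rest on an interaction test, because significance in one stratum and not in the other is not a test of the difference.

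The cost is SAP wording only. The single-method p-values by baseline stratum are given up, and the interaction shows whether the advantage of one method over the other varies with dryness, not whether each method works better in drier eyes. Answering that second question would need an additional unstimulated reading, which is a protocol change.
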